### **8.12.3. Vital Signs**

Descriptive statistics will be provided for vital sign data (systolic and diastolic blood pressure, heart rate, and respiratory rate) presented as both actual values and changes from baseline over time.

A listing of all vital signs will be provided by patient.

### **8.12.4. Electrocardiograms**

Descriptive statistics will be provided for 12-lead ECG findings (heart rate, QRS, PR, RR, QT, and QTcF) and changes from baseline for each scheduled visit in the Safety Population.

Change from baseline will be calculated for each patient as the post-baseline value minus the baseline value. Boxplots by treatment group of the ECG parameters will also be provided for the baseline and post-baseline ECG assessments.

The number and percentage of patients with notable ECG changes in maximum QTcF ( $> 450$  msec,  $> 480$  msec, and  $> 500$  msec) over all post-baseline evaluations, as well as in QTcF maximum changes from baseline ( $> 30$  msec and  $> 60$  msec) over all post-baseline evaluations will be summarized by treatment group.

All 12-lead ECG findings will be listed by patient.

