16. Likely to require the use of an antibiotic for cUTI or AP prophylaxis during the patient's participation in the study (from randomization through the LFU Visit);
17. Known history of human immunodeficiency virus infection and known recent CD4 count $<200/\text{mm}^3$ within the last year;
18. Presence of significant immunodeficiency or an immunocompromised condition, including hematologic malignancy, bone marrow transplant, or receiving immunosuppressive therapy such as cancer chemotherapy, medications for the rejection of transplantation, and long-term use of systemic corticosteroids (equivalent to ≥ 20 mg/day of prednisone or systemic equivalent for ≥ 2 weeks);
19. Presence of neutropenia (absolute neutrophil count $<1000/\text{mm}^3$) obtained from a local laboratory at Screening;
20. Presence of thrombocytopenia (especially in patients diagnosed with disseminated intravascular coagulation or at risk of serious bleeding) $<50,000$ platelets/ mm^3 obtained from a local laboratory at Screening;
21. A QT interval corrected using Fridericia's formula (QTcF) >480 msec;
22. History of significant hypersensitivity or allergic reaction to any β -lactam, any contraindication to the use of imipenem/cilastatin based on local approved prescribing information (eg, Summary of Medicinal Product Characteristics), any contraindication to the excipients used in the respective formulations, or any contraindication to the use of β -lactam antibiotics;
23. Participation in a clinical study involving investigational medication or an investigational device within the last 30 days or 5 half-lives, whichever is longer, prior to randomization;
24. Unable or unwilling, in the opinion of the Investigator, to comply with the protocol; or
25. Any patients previously randomized in this study.

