8.8 Electrocardiograms

Twelve-lead ECGs will be performed at baseline at Screening and repeated as close as possible to the end of the infusion of study drug administration on the day on which the post-dose PK samples are drawn (Day 3, Day 4, or Day 5; day selected at the discretion of the Investigator). All 12-lead ECGs will be performed after the patient has been in a supine position for at least 10 minutes. The value at Screening will be used for assessing the QTcF exclusion criterion. All 12-lead ECGs will be performed and read locally. The following ECG parameters will be recorded:

- Heart rate,
- QRS interval,
- PR interval,
- RR interval,
- QT interval, and
- QTc interval.

All ECGs will be evaluated for the presence of abnormalities by a qualified local physician. The ECGs will be classified as one of the following:

- Normal,
- Having a not clinically significant abnormality, or
- Having a clinically significant abnormality.

An example of a clinically significant abnormality may be a corrected QTcF >480 msec.

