9.2.4 Analysis of Safety

All patients who receive any amount of study drug (Safety Population) will be included in the safety analyses. Patients who received the wrong study drug for their entire course of treatment will be analyzed in the group based on the drug received. Safety endpoints include the assessment of TEAEs and the evaluation of changes from baseline in safety laboratory test results, ECGs, vital signs, and physical examinations.

Adverse events will be coded using version 20.0 (or higher) of the Medical Dictionary for Regulatory Activities (MedDRA). The number and percentage of patients in each treatment group reporting at least 1 occurrence of a TEAE for each unique system organ class and preferred term will be tabulated. A TEAE is defined as an adverse event occurring on or after the administration of the first dose of study drug. Treatment-emergent adverse events will also be tabulated by treatment group, severity, and the relationship to study drug as assessed by the Investigator. The number and percentage of patients in each treatment group reporting at least 1 occurrence of a treatment-emergent SAE will be tabulated. The number and percentage of patients (in each treatment group) prematurely discontinuing study drug treatment due to a TEAE will be tabulated by system organ class and preferred term.

Safety laboratory data will be presented by descriptive statistics of the post-baseline value and the change from baseline, as well as the number and percentage of patients with potentially clinically significant laboratory values. Descriptive statistics of vital signs and ECG parameters and the change from baseline will also be presented. An outlier analysis of the ECG parameters will be conducted.

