18. The 12-lead ECG will be performed at baseline at Screening and repeated as close as possible to the end of the infusion of study drug administration on the day on which post-dose PK samples are drawn (Day 3, Day 4, or Day 5). The day on which the post-dose PK samples are drawn is at the discretion of the Investigator. All 12-lead ECGs will be performed after the patient has been in a supine position for at least 10 minutes.
19. Consult the Medical Monitor and local cardiologist in cases of clinically significant abnormal findings (eg, a QTcF >480 msec).
20. If baseline blood cultures were positive, repeat blood cultures should be obtained daily until negative or if the patient is a treatment failure.
21. An adequate clean-catch urine specimen for culture (or other appropriate method to collect a urine culture that minimizes risk of bacterial contamination) should be obtained at the specified time points. At any point in the study, if a patient fails while on therapy, a urine specimen should be obtained.
22. A repeat urine sample for culture must be obtained prior to the start of study drug treatment for any patient enrolled in the study who has received a single dose of a short-acting antibiotic in the 24 hours prior to randomization or for patients who failed preceding antimicrobial therapy. This sample should be taken as close to randomization as possible (within 2 hours prior to randomization, if possible).
23. Study drug should be administered q6h for a minimum of 7 days (28 doses), as described in the protocol.
24. All patients will be administered impipenem/cilastatin q6h.
25. Adverse events should be captured as described in the protocol.
26. PK samples will be collected immediately prior to the first dose of study drug on Day 1 and post-dose of any study drug infusion on Day 4 ( $\pm 1$  day) at the end of the infusion when the infusion pump is turned off, 0.5 hours after the end of the infusion, 2 hours after the end of the infusion, and 3 hours after the end of the infusion (prior to the start of the next infusion).

ECG = electrocardiogram; EOT = End of Treatment; IV = intravenous; LFU = Late Follow-up; PK = pharmacokinetics; q6h = every 6 hours; QTcF = QT interval corrected using Fridericia's formula; TOC = Test-of-Cure.

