### **8.3. Baseline Definition**

For microbiological data, baseline pathogen(s) are determined from all specimens collected prior to the first dose of study drug.

For all efficacy and safety endpoints, baseline is defined as the last measurement or assessment prior to the first dose of study drug.

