### **8.12.2. Clinical Laboratory Evaluations**

Laboratory test results (hematology, serum chemistry, and urinalysis) at each scheduled visit and change from baseline will be summarized by treatment group.

Shift tables from baseline to each scheduled post-baseline visit will be provided for selected chemistry parameters (ALT, AST, total bilirubin, creatinine, creatine kinase, ALP, potassium) and hematology parameters (hematocrit, hemoglobin, platelets, white blood cell count and differential). For chemistry parameters, the following categories will be used: < the lower limit of normal (LLN), normal, > the upper limit of normal (ULN) to  $\leq 3 \times \text{ULN}$ ,  $> 3 \times \text{ULN}$  to  $\leq 5 \times \text{ULN}$ ,  $> 5 \times \text{ULN}$ , and missing. For hematology parameters, the following categories will be used: low, normal, high, and missing. Boxplots over time by treatment group of total white blood cell and absolute neutrophil counts will also be provided.

The number and percentage (based on the number of patients with a normal level at baseline) of patients in each treatment group with an ALT ( $> 3 \times \text{ULN}$ ,  $> 5 \times \text{ULN}$ , and  $> 10 \times \text{ULN}$ ), an AST ( $> 3 \times \text{ULN}$ ,  $> 5 \times \text{ULN}$ , and  $> 10 \times \text{ULN}$ ), an ALT or AST  $> 3 \times \text{ULN}$ , and a total bilirubin ( $> 1.5 \times \text{ULN}$  and  $> 2 \times \text{ULN}$ ) will be presented by study visit. A listing of patients who meet the laboratory criteria for Hy's law will also be provided. The laboratory criteria for Hy's law is defined as ALT or AST  $> 3 \times \text{ULN}$ , ALP  $\leq 2.0 \times \text{ULN}$ , and total bilirubin  $> 2 \times \text{ULN}$ . A listing will also be provided for the potentially clinically significant (PCS) values for the above parameters.

All clinical laboratory data will be listed. Values outside the normal ranges will be flagged.

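### The >450 msec row of the QTcF outlier table counts patients who were already above 450 msec at entry as having a notable change; the effect is confined to that descriptive row (minor).

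*SAP*

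**What the plan says.** Eligibility: protocol section 4.2, exclusion 21, bars "A QT interval corrected using Fridericia's formula (QTcF) >480 msec". Protocol section 8.8 adds: "The value at Screening will be used for assessing the QTcF exclusion criterion". Values of 451 to 480 msec are therefore eligible.

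Schedule: note 18 to SAP Table 1 states "The 12-lead ECG will be performed at baseline at Screening and repeated as close as possible to the end of the infusion", on the day of post-dose PK sampling (Day 3, 4 or 5). That gives one baseline ECG and one scheduled on-treatment ECG per patient. SAP section 8.3 sets the reference value: "baseline is defined as the last measurement or assessment prior to the first dose of study drug". For the ECG this is normally the Screening tracing.

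Analysis: protocol section 9.2.4 promises that "An outlier analysis of the ECG parameters will be conducted" but does not define it, so SAP section 8.12.4 is the only definition. It lists "The number and percentage of patients with notable ECG changes in maximum QTcF" at >450, >480 and >500 msec "over all post-baseline evaluations, as well as in QTcF maximum changes from baseline" of >30 and >60 msec. No baseline restriction is attached to the absolute thresholds. The section also gives descriptive statistics for change from baseline, boxplots of baseline and post-baseline values by group, and a listing of all ECG findings by patient.

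Comparison within the SAP: for liver-test outliers, section 8.12.2 takes the percentage "based on the number of patients with a normal level at baseline", and it specifies shift tables from baseline for selected chemistry and hematology parameters. The ECG section has neither.

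**The concern.** The lowest outlier threshold (450 msec) lies below the entry limit (480 msec). The band in between is both an admissible starting value and an outlier category. A patient in that band who does not change, or who improves, is counted under a label that speaks of change.

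Safety versus placebo is the study's primary objective, and the arms are small. A few patients who entered above 450 msec and happened to fall unevenly between the arms could create or mask a difference in this row, which also contains everyone in the >480 and >500 rows.

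The change rows do not replace the missing information. A rise from 445 to 470 msec (+25 msec) is a new crossing of 450 but appears in neither the >30 nor the >60 row. As planned, new crossings can be told apart from pre-existing values only by reading the listing.

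**Working it through.** The plan states no figure for this table, so there is none to reproduce.

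**Step 1. Compare the thresholds.**
- Entry: QTcF ≤480 msec. Outlier rows: >450, >480, >500 msec.
- >450 row: values in 450 < QTcF ≤ 480 can exist at entry, so the row mixes pre-existing and new values.
- >480 and >500 rows: no eligible patient starts above 480 msec on the Screening ECG, so any count is new unless there was a protocol deviation.
- Example: 465 msec at Screening and 460 msec on treatment is a change of 460 − 465 = −5 msec, yet it is counted in the >450 row.

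**Step 2. Group sizes.** About 80 patients at 2:1 (protocol section 9.2.6; SAP section 4): 80 × 2/3 = 53.3 and 80 × 1/3 = 26.7, taken as 53 and 27.

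**Step 3. Size of the overlap.** The documents give no QTcF distribution. Assumed: normal values, mean 410–420 msec, total SD (s) 20–25 msec, within-patient SD (w) 8–15 msec, no drug effect, one baseline and one post-baseline ECG, baseline truncated at 480 msec. The correlation between the two ECGs is r = 1 − w²/s².

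One case in full, with mean 420, s = 25, w = 12:
- r = 1 − 144/625 = 0.770.
- Share entering above 450 msec: [Φ(2.4) − Φ(1.2)] / Φ(2.4) = (0.9918 − 0.8849) / 0.9918 = 0.108.
- From the truncated bivariate normal: above 450 msec at both ECGs 0.0560; above 450 msec post-baseline 0.1085.
- Share of the row that was pre-existing: 0.0560 / 0.1085 = 52%.
- Expected patients above 450 msec at both ECGs: 53 × 0.0560 = 3.0 and 27 × 0.0560 = 1.5.

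Extremes of the assumed range:

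| Mean, s, w (msec) | Enter >450 | Post-baseline >450 | >450 at both | Pre-existing share of row | Of 53 | Of 27 |
|---|---|---|---|---|---|---|
| 410, 20, 15 | 2.25% | 2.27% | 0.32% | 14% | 0.2 | 0.1 |
| 420, 25, 8 | 10.8% | 10.8% | 7.26% | 67% | 3.9 | 2.0 |

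**Step 4. Chance imbalance at entry.** If a proportion q enters above 450 msec, with independent binomial counts in arms of 53 and 27, the probability that the two observed proportions differ by at least 10 percentage points is 4.7% for q = 5%, 14.5% for q = 10% and 27.8% for q = 20%. The assumptions in Step 3 imply q of about 2% to 11%. The imbalance carried into the >450 row is smaller, because some of these patients fall to 450 msec or below at the second ECG.

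**Step 5. What a new-crossing count would show.** Over the same grid with no drug effect, the >450 row as written holds 2.3% to 11.0% of patients. The proportion newly above 450 msec among those at or below 450 msec at baseline is 1.2% to 7.3%.

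**The case against.** The case for leaving the table alone is substantial. It is descriptive, with no ECG hypothesis test and no stopping rule attached. Placebo patients are counted by the same rule. The section already separates absolute maxima from changes of >30 and >60 msec, plots baseline beside post-baseline values by group, and lists every ECG. With about 80 patients and one scheduled on-treatment tracing, a reader can check each patient above 450 msec by hand. A new-crossing count would also remain noisy: 449 to 451 msec would qualify, and Step 5 shows that much of the row survives with no drug effect.

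All of this stands and limits the weight of the point. It does not repair the row. The label still describes unchanged values as changes, and no table shows new crossings.

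A reader might infer more than the documents support:
- That the table is biased for or against the active drug. Identical counting in a randomised comparator leaves chance imbalance only.
- That everyone who enters at 451–480 msec is miscounted. Under the assumptions above that would be about 1.2–5.7 of 53 and 0.6–2.9 of 27, but only those still above 450 msec at the second ECG reach the row.
- That the wrong heart-rate correction will be analysed, because protocol section 8.8 lists a QTc interval without a formula. Exclusion 21 and SAP section 5.2.4 both name QTcF, and QT and RR are recorded, so this is a wording mismatch. The documents give no basis for sizing any shift from it.
- That the ECG is timed to detect a QT effect. The documents give the timing (close to the end of infusion) but not that purpose.

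**Conclusion.** The point holds for one row. SAP section 8.12.4 counts any post-baseline QTcF above 450 msec as a notable change although patients may enter at up to 480 msec, and it omits the kind of baseline restriction that section 8.12.2 applies to liver tests. This follows from the text alone.

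Its size rests on the assumed QTcF distribution: roughly 0.2–3.9 of 53 and 0.1–2.0 of 27 patients, or 14–67% of those in the row. The width of that range reflects how little is known beforehand about within-patient variability. The >480 and >500 rows and the change-from-baseline rows are unaffected, and no conclusion of the trial depends formally on this table. Severity is minor; the reason to act is that the correction is nearly free and concerns the primary (safety) objective.

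**What to change.** In SAP section 8.12.4:
1. Keep the >450, >480 and >500 msec thresholds, but describe them as maximum post-baseline values. Reserve the word change for the >30 and >60 msec rows.
2. Add a shift table of baseline by maximum post-baseline QTcF, by treatment group, with categories ≤450, >450–480, >480–500 and >500 msec. Report the number and percentage newly above 450 msec, with patients at or below 450 msec at baseline as the denominator, in line with section 8.12.2.
3. Optionally, state that QTcF is derived for every ECG from the recorded QT and RR. This settles the difference in wording between protocol section 8.8 and SAP section 5.2.4.

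The cost is a wording change and one extra table, with no new data and no change to eligibility or conduct. The new-crossing counts will be smaller than the counts under the present wording and will still rest on a single ECG before and, as scheduled, a single ECG during treatment.

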**8.12.5. Physical Examination**

Physical examination findings will be listed by patient.

**8.13. Pharmacokinetic Analyses**

The pharmacokinetic analyses will be performed by another vendor and reported separately.

**8.14. Interim Analysis**

No interim analysis of efficacy has been planned.
